1. BACKGROUND

Alcohol use results in a high healthcare and economic burden. Alcohol use is the third leading cause of premature death in the UK¹ and is the main driver of chronic liver disease, which is estimated to affect 600,000 people in England alone.² Alcohol was involved in over 1.1 million unplanned hospital admissions in 2017/8, of which 63,000 were due to alcohol-related liver disease (ArLD), and led to 25,000 deaths.² Alcohol-related healthcare costs £3.5 billion to the NHS directly and up to £52 billion to the UK economy annually.³

ArLD reduces patients' quality of life and survival. It is caused by long-term alcohol consumption, usually with physiological and psychological dependence, characterised by liver damage (fibrosis) leading to cirrhosis, which impacts patients' quality of life⁴ (QoL) and survival.⁵ Alcohol dependence is characterised by craving, tolerance, a preoccupation with alcohol and continued drinking in spite of harmful consequences.⁶ The only effective treatment to prevent progression of liver damage is reducing or ceasing alcohol consumption.⁵ Patients who continue to drink heavily develop progressive liver damage⁷ and have a higher risk of death.⁸ In the most affected group of ArLD patients, those with an acute inflammatory liver injury termed alcoholic hepatitis (AH), two-thirds of patients who survive to hospital discharge relapse to alcohol consumption within six months and have a three- to four-fold risk of death within one year.^{9,10} A typical district general hospital in the UK will treat approximately 200 ArLD patients annually but in more deprived, large, urban communities such as in Plymouth, Bristol and Leeds admissions are above average.²

Admission to hospital is an opportune time for intervention. Unplanned hospital admission is a crisis point in the ArLD patient's journey. Research on smoking cessation, weight loss, and alcohol reduction shows that medical crises, including disease diagnosis and hospital admission, provide an opportunity for intervention where behaviour change is more likely to result.¹¹⁻¹⁴

Treatment as usual (TAU) is a brief intervention, a form of motivational interviewing (MI),

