4. OBJECTIVES AND OUTCOME MEASURES / ENDPOINTS

Research question for the future definitive trial:

In patients with ArLD and alcohol dependence admitted to hospital, does addition of FIT to treatment as usual, compared to treatment as usual alone, lead to reduced alcohol consumption and alcohol-related harm over 6 months?

To finalise the design of a definitive trial to answer this question, we will firstly undertake this pilot trial with the following objectives.

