17. STATISTICS AND DATA ANALYSIS

17.1. Target sample size and justification

One of the key objectives of this pilot study, to inform the definitive trial, is whether patients can be successfully recruited and followed-up. We estimate that across all three sites, 24 potentially eligible ArLD patients are admitted per month. Allowing for staggered site set-up and a 7-month recruitment window, we anticipate screening ~150 patients; with a conservative recruitment rate of those screened of 60%, our recruitment target is 90 participants (~30/site).

This recruitment target will allow estimation of the overall retention rate with a 95% confidence interval (CI) of at least $\pm 11\%$. Assuming a non-differential retention rate of 75% at 6-month follow-up, indicates primary outcome data will be available from a minimum of 33 participants within each allocated group, allowing appropriate estimation of key components, such as the variability in the primary outcome, to inform the sample size calculations for the definitive trial.

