3.5 SAMPLE SIZE CALCULATION

One of the key objectives of this pilot study, to inform the definitive trial, is whether patients can be successfully recruited and followed-up. We estimate that across all sites, 24 potentially eligible ArLD patients are admitted per month. Our total recruitment target is 90 participants.

This recruitment target will allow estimation of the overall retention rate with a 95% confidence interval (CI) with precision of at least $\pm 11\%$. Assuming a non-differential retention rate of 75% at the 6-month follow-up (the anticipated primary endpoint for a definitive trial), indicates primary outcome data will be available from a minimum of 33 participants within each allocated group. This will enable appropriate estimation of key components, such as the variability in the proposed primary outcome, to inform the sample size calculations for the definitive trial.

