5.1.2 Participants who Discontinue, Withdraw or are Lost to Follow-up

It is possible that participants will withdraw consent part way through the trial, or their treatment may be discontinued due to medical reasons. It is unlikely in this trial that a participant will be discontinued on medical grounds (for either allocated group), but for reasons such as injury, some participants may not be able to complete the trial. Participants who discontinue will be categorised as follows:

- Continue to consent for follow-up and data collection
- Consent to use pre-collected data only
- Complete withdrawal of consent to use any data

Reasons for withdrawal or loss to follow up will be summarised where reported, at each stage of the process (**Error! Reference source not found.**), including withdrawal prior to randomisation, participants who did not receive their allocated treatment, non-completion of treatment, lost to follow-up.

Participants who withdraw from the study, or whose treatment is discontinued on medical grounds, will not be replaced although their available data will be used unless they have specifically requested for it to be removed from the database. The extent of discontinuation, withdrawal and loss to follow up will be used to inform the design of the fully powered subsequent study, predominantly to ensure a sufficiently powered trial after allowing for losses to follow-up.

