5.5 PROGRESSION TO DEFINITIVE TRIAL

The progression criteria in Table 2 are proposed for consideration as part of the decision on whether or not to progress to planning a definitive trial. If the study delivers results on all of the progression criteria in the green column, it is intended that this will result in the planning of a definitive trial. If some criteria are in the amber column, modification of the trial design will be required before considering progression. If some criteria fall in the red column, the trial team will consider all options, including not progressing to a definitive trial.

Criteria	Red	Amber	Green
Percentage recruited from patients approached by research team (for discussion of informed consent)	<40	40 – 60	>60
Percentage of intervention participants completing FIT session 1 and at least one of FIT session 2 or FIT session 3	<50	50 – 70	>70
Percentage of all participants followed-up at proposed primary endpoint of 180 days	<60	60 – 80	>80
Percentage of all participants providing valid data for the proposed primary outcome of alcohol use at proposed primary endpoint of 180 days	<55	55 – 75	>75

Table 2: Proposed progression criteria for planning a definitive trial

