Fibrosis			
Cirrhosis			
Child-Pugh Score			
Mean (SD) [range]			
Median (IQR)			
MELD Score			
Mean (SD) [range]			
Median (IQR)			

*Participants can provide data in more than one category – percentages will not necessarily add to 100%

Table 10: Summary statistics for the proposed primary and secondary outcome measures by allocated group

Variable	Time point	TAU			FIT + TAU		
		N	Mean (SD) (95% CI)/Median [IQR]	Range	N	Mean (SD) (95% CI) /Median [IQR]	Range
Alcohol Use (grams of pure alcohol/ week)	baseline						
	28 (±7) days						
	90 (±7) days						
	180 (±14) days						
SADQ Score	baseline						
	28 (±7) days						
	90 (±7) days						
	180 (±14) days						
WEMWBS	baseline						
	28 (±7) days						
	90 (±7) days						
	180 (±14) days						
SWEMWBS	baseline						
	28 (±7) days						
	90 (±7) days						
	180 (±14) days						
Ethyl Glucuronide (µg/L)	180 (±14) days						
Ethyl Sulphate (µg/L)	180 (±14) days						
Re- hospitalisation*	180 (±14) days						

* Rates and corresponding confidence intervals given for re-hospitalisation

Table 11: Summary statistics for the changes between baseline and 28, 90, and 180 day assessments for proposed primary and secondary outcomes including only those participants who complete all follow-up visits

Variable	Time point	TAU			FIT + TAU		
		N	Mean (SD) Change From Baseline (95% CI)/Median [IQR]	Range	N	Mean (SD) Change From Baseline (95% CI) /Median [IQR]	Range
Alcohol Use (grams of pure alcohol/ week)	28 (±7) days						
	90 (±7) days						
	180 (±14) days						
SADQ Score	28 (±7) days						
	90 (±7) days						
	180 (±14) days						
WEMWBS	28 (±7) days						
	90 (±7) days						
	180 (±14) days						
SWEMWBS	28 (±7) days						
	90 (±7) days						
	180 (±14) days						

Table 11b: Proportion of participants who completed TLFB assessment and with no alcohol consumption as calculated from TLFB

Variable	Time point	TAU	FIT + TAU
		N (% of participants with complete TLFB)	N (% of participants with complete TLFB)
Participants with zero alcohol consumption	Baseline		
	28 (±7) days		
	90 (±7) days		
	180 (±14) days		

Table 12: Re-hospitalisations by allocated group

Re-hospitalisation	TAU N (%)				FIT + TAU N (%)			
	0	1	2	>2	0	1	2	>2
No. of re-admissions								
By 28 (± 7) days								
By 90 (± 7) days								
By 180 (± 14) days								

Table 13: Proportion of participants who relapse and time to relapse to alcohol use by allocated group

	TAU	FIT + TAU
N (%) who relapsed by:		
28 (± 7) days		

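### Deaths leave the drinking and abstinence results and are planned for reporting only by FIT received, so an arm with more deaths can look more abstinent

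*SAP*

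**What the plan says.** **Abstinence.** SAP 3.4.3 promises the proportion reporting no alcohol in the preceding week at each follow-up visit, by allocation. Table 11b sets the denominator. It is titled "Proportion of participants who completed TLFB assessment and with no alcohol consumption as calculated from TLFB", and its column heads take percentages of those with a complete timeline follow-back (TLFB).

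**Alcohol use and change.** SAP 4.2 leaves out anyone whose score cannot be imputed at the time point concerned. SAP 4.7.1 does not impute a missed visit. Table 11 (change from baseline) is limited to those who completed every follow-up visit. None of these rules separates death from other missing data.

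**Deaths by group.** In the SAP's own rules, death appears only as a seriousness criterion (5.4). SAP 4.2 and 5.4 group safety data by whether at least one FIT session was received. Protocol 10.5.1 allows session 1 at any time up to discharge, so a FIT-allocated inpatient who dies before it is shown under TAU.

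**Re-hospitalisation.** Table 12 counts 0, 1, 2 or more than 2 re-admissions, with no stated denominator and no rule for death.

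**Progression.** Row 3 of Table 2 (SAP 5.5) is the "Percentage of all participants followed-up at proposed primary endpoint of 180 days", green above 80%. Row 4 is valid alcohol data at day 180, also over all participants, green above 75%. Neither document defines what counts as followed up.

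**The concern.** The definitive trial is to ask whether adding FIT will "lead to reduced alcohol consumption and alcohol-related harm over 6 months". Death is the gravest such harm. Protocol 1 says that patients with alcohol-related liver disease who continue to drink heavily have a raised risk of it. If deaths concentrate among drinkers, removing them leaves a survivor group that is more abstinent than the arm as randomised, and more so in the arm with more deaths.

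The preliminary assessment of FIT (SAP 5.3) and the standard deviation and correlation for the definitive trial (SAP 5.6) come from the same reduced set. Because deaths are grouped by FIT received, a reader cannot set deaths by allocated arm beside the drinking results. In the progression table, a percentage lowered by deaths could be mistaken for failed tracing.

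**Working it through.** **Inputs from the documents**
- Total 90, allocated 1:1, so 45 per arm: "our recruitment target is 90 participants (~30/site" (Protocol 17.1; ratio in 6.1).
- Retention: "Assuming a non-differential retention rate of 75% at the 6-month follow-up" (SAP 3.5).
- Green thresholds: above 80% followed up, above 75% with valid alcohol data (SAP 5.5).

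**Inputs assumed, because the documents give none**
- Deaths by day 180: 2 to 10 per arm for abstinence; 0 to 18 in total for progression.
- Abstinence: 15 of 45 per arm. Re-admissions: 15 against 18.

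**1. The plan's own figures.** The widest 95% half-width at n = 90 is 1.96 × √(0.5 × 0.5 / 90) = 10.3 points (exact interval 10.7), so ±11% holds. Evaluable per arm: 0.75 × 45 = 33.75, so at least 33 holds. Neither figure separates deaths from other loss.

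**2. Abstinence.** Let A be the number alive and abstinent and D the number of deaths, with no other missing data. Table 11b gives A/(45 − D); over all randomised the figure is A/45. Take A = 15 in each arm, all deaths among drinkers, and 2 deaths in the comparison arm (15/43 = 34.9%).

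| Deaths in other arm | Table 11b, other arm | Apparent difference (points) | All randomised, both arms |
|---|---|---|---|
| 2 | 15/43 = 34.9% | 0.0 | 33.3% |
| 4 | 15/41 = 36.6% | +1.7 | 33.3% |
| 6 | 15/39 = 38.5% | +3.6 | 33.3% |
| 8 | 15/37 = 40.5% | +5.7 | 33.3% |
| 10 | 15/35 = 42.9% | +8.0 | 33.3% |

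The sign can reverse. With 8 deaths and 14 abstinent against 2 deaths and 15 abstinent, Table 11b gives 14/37 = 37.8% against 34.9%, but 14/45 = 31.1% against 33.3% of those randomised.

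**3. The condition this needs.** If deaths fall in proportion to drinking status (two-thirds drinkers), 6 deaths remove 2 abstainers: 13/39 = 33.3%. The comparison arm is also 33.3% (14.33/43, in expectation). Table 11b does not shift. Alive and abstinent over all randomised would then be 13/45 = 28.9% against 14.33/45 = 31.9%, because it counts the deaths themselves. The two rows answer different questions, and both are needed.

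**4. Re-hospitalisation.** Assume 15 against 18 re-admitted, and 8 against 2 who die without re-admission. Counting the dead as 0 re-admissions gives 15/45 = 33.3% against 18/45 = 40.0% (−6.7 points). Re-hospitalised or died gives 23/45 = 51.1% against 20/45 = 44.4% (+6.7). With 4 against 2 deaths the second comparison is 19/45 = 42.2% against 44.4% (−2.2), so reversal needs a marked imbalance.

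**5. Progression, row 3.** Green needs 73/90 = 81.1%, since 72/90 is exactly 80.0%.

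| Deaths | Share of survivors needed for green |
|---|---|
| 0 | 73/90 = 81.1% |
| 5 | 73/85 = 85.9% |
| 9 | 73/81 = 90.1% |
| 14 | 73/76 = 96.1% |
| 18 | unattainable (maximum 72/90 = 80.0%) |

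With 9 deaths and 71 survivors followed, the result is 71/90 = 78.9% (amber), although 71/81 = 87.7% of those alive were followed.

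**The case against.** The case for leaving the plan alone has real substance.

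- **Modest role and size.** Table 11b is an example table in a pilot without hypothesis tests. Its denominator is printed, and zero drinking has no row in the between-group tables (14 to 17). The 3.6-point shift is small beside its uncertainty: 1.96 × √(0.385 × 0.615/39 + 0.349 × 0.651/43) is about 21 points. This stands and limits the weight of the point. It does not make the denominator neutral.
- **Mortality.** A reader might take from Protocol 1 that anyone who relapses will "have a three- to four-fold risk of death within one year". That figure belongs to alcoholic hepatitis patients who survive to discharge. The trial also admits people with fatty infiltration only and excludes life expectancy under 6 months. Only the general statement about continued heavy drinking supports the direction of bias.
- **Not all data vanish.** Day 28 and day 90 data collected before a death stay in those summaries (though not in Table 11), and a relapse reported before death still counts. Protocol 17.4 compares those lost with completers. Deaths are not hidden: they are reported as serious adverse events, and that grouping departs from allocation only for FIT-allocated participants with no session or for crossover.
- **Participant flow.** A reader might fault SAP 5.1.2 for having no death category. Its categories are states of consent to data use, where death does not belong, and reasons for loss are summarised separately. The CONSORT figure is not shown and may contain a box for deaths.
- **Progression.** A reader might conclude that Table 2 uses the wrong denominator. It does not: all participants is the right total for planning a sample size, and the dead supply no day-180 data. That deaths count as not followed up is the natural reading, not a written rule.
- **Re-hospitalisation.** Placing someone who died in the 0 column is a possibility left open by silence. Hospital records are a permitted source, so an admission ending in death can be counted.

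**Conclusion.** The point holds for the drinking outcomes, where exclusion of the dead follows from the written rules, and for the absence of any planned table of deaths by allocated arm. In the illustration the distortion of Table 11b runs from 1.7 to 8.0 points as deaths rise from 4 to 10 in one arm against 2 in the other. This assumes 15 of 45 abstinent in each arm, every death in a drinker, and no other missing data. It is nil if deaths are balanced or unrelated to drinking. The documents give neither mortality nor abstinence rates, so they do not show that bias occurred or which arm it would favour.

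Re-hospitalisation and progression are matters of clarification, because the relevant terms are undefined. The documents do not support saying that Table 2 is wrong or that death is ignored throughout. A change is worth making because it is cheap and adds the comparison by allocation that the present tables cannot give.

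**What to change.** 1. Report deaths by day 28, 90 and 180 by allocated arm, in addition to the safety listing by FIT received.
2. Add to Table 11b a row for *alive and no alcohol in the previous 7 days*, over all randomised. Score death as not achieved, and show untraced survivors separately. Keep the existing row.
3. State the denominator of Table 12 and report *re-hospitalised or died* beside re-hospitalisation.
4. Keep rows 3 and 4 of Table 2 on all participants. Beside each, show the percentage of those alive at day 180, so that an amber result caused by deaths is not read as failed tracing.

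The cost is a few descriptive rows. Deaths are already collected as serious adverse events (Protocol 16), and Protocol 10.6 allows the GP to be asked about a participant who cannot be reached. Anyone whose vital status remains unknown should be shown as such. Rows added after database lock should be labelled post hoc; Table 11b was itself added then, with the statisticians unblinded (SAP revision history).

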3.4.3 Participant-Reported and Clinical Outcome Measures

Outcome Measure	Baseline	28 days post-baseline	90 days post-baseline	180 days post-baseline
Alcohol use	X	X	X	X
SADQ	X	X	X	X
WEMWBS	X	X	X	X
SWEMWBS	X	X	X	X
Re-hospitalisation		X	X	X
Alcohol relapse		X	X	X
Alcohol metabolites				X
EQ-5D-5L*	X	X	X	X
Resource Use Questionnaire*	X		X	X

* please see separate HEAP

Table 1: Table detailing the timing of participant reported and other clinical outcomes

The participant-reported and clinical outcome measures listed in Table 1 will be collected in the pilot trial to help inform appropriate primary and secondary outcome measures for the definitive trial and to allow a preliminary assessment of FIT intervention in the ArLD population. The proposed primary outcome for a future definitive trial is change in self-reported alcohol use (grams of pure alcohol/week) between baseline and 180 (± 14) days post-baseline. The Timeline Follow-Back technique¹⁵ will be used to determine a participant's alcohol use during the 7 days immediately prior to: their hospital admission (baseline) and 28, 90 and 180 days post-baseline. The completeness of the Timeline Follow-Back data will also be assessed. We will report, for each visit after baseline, the number and proportion of participants who reported not taking alcohol 7 days prior to the assessment day by allocation.

Proposed secondary outcomes for a future definitive trial are the:

- *Severity of Alcohol Dependence Questionnaire (SADQ)*¹⁴ – This questionnaire consists of 20 items and covers the following areas of the dependency syndrome:
 - physical withdrawal symptoms; affective withdrawal symptoms
 - relief drinking
 - frequency of alcohol consumption
 - speed of onset of withdrawal symptoms.Each item of the questionnaire is scored between 0 (almost never) and 4 (nearly always)
- *Warwick-Edinburgh Mental Wellbeing Scale (WEMWBS)*¹⁷ – This questionnaire is a measurement of mental wellbeing, consisting of 14 items each with a score between 1 (None of the time) and 5 (all of the time)
- *Short Warwick-Edinburgh Mental Wellbeing Scale (SWEMWBS)*¹⁸ - This questionnaire is the short version of WEMWBS, consisting of 7 of the items from the full WEMWBS
- *Re-hospitalisation within 180 days post baseline* – Self-reported by participants or determined using hospital records at participating sites

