5.6 SAMPLE SIZE FOR DEFINITIVE TRIAL

One of the key purposes of a pilot study is to obtain data to inform the sample size calculation for a definitive trial. To assist with future sample size calculations, we will calculate, overall and by allocated group:

- the standard deviation for the proposed primary outcome of alcohol consumption (grams consumed of pure alcohol in the previous week)
- the correlation coefficient between baseline and (i) 180 day assessment and (ii) change between baseline and 180 day assessment for the proposed primary outcome of grams consumed of pure alcohol in the previous week

Point estimates will be presented alongside two-sided 80% and 90% confidence intervals.

Indicative sample sizes for a definitive trial with alcohol use at 180 days as the primary outcome will then be produced, conservatively using the upper bounds from the confidence intervals for the estimated standard deviation. Additional sample size scenarios will consider adjustment for baseline alcohol use (i.e. using an analysis of covariance approach) and will use the lower bound from the confidence intervals for the correlation coefficient.

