Table 17: Between-group differences and confidence intervals for of change from baseline for proposed primary and secondary outcome measures, adjusted for stratification variables (dichotomised baseline SADQ score and site)

Variable	Time Point	Adjusted Mean Between-group Difference of Change From Baseline	Adjusted 95% CI	Adjusted 85% CI	Adjusted 75% CI
Alcohol Use (grams of pure alcohol/ week)	28 (± 7) days				
	90 (± 7) days				
	180 (± 14) days				
SADQ Score	28 (± 7) days				
	90 (± 7) days				
	180 (± 14) days				
WEMWBS	28 (± 7) days				
	90 (± 7) days				
	180 (± 14) days				
SWEMWBS	28 (± 7) days				
	90 (± 7) days				
	180 (± 14) days				
Ethyl Glucuronide ($\mu\text{g/L}$)	180 (± 14) days				
Ethyl Sulphate ($\mu\text{g/L}$)	180 (± 14) days				

Table 18: Estimates of standard deviations of proposed primary outcome (alcohol use) for informing sample size calculations for a definitive trial

Parameter	Point Estimate	80% CI*	90% CI*
Standard deviation of alcohol use at baseline			
Standard deviation of alcohol use at 180 (± 14) days assessment			
Standard deviation of change in alcohol use between baseline and 180 (± 14) days assessment			

* upper bound of two-sided confidence interval relevant as conservative estimate for sample size calculations

Table 19: Estimates of correlation coefficients for proposed primary outcome (alcohol use) for informing sample size calculations for a definitive trial

Parameter	Point Estimate	80% CI*	90% CI*
Correlation coefficient between baseline and 180 (± 14) days assessment of alcohol use			
Correlation coefficient between baseline and change between baseline and 180 (± 14) days assessment of alcohol use			

* lower bound of two-sided confidence interval relevant as conservative estimate for sample size calculations

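### The rule that the lower confidence bound is conservative points the wrong way for the baseline-versus-change correlation in SAP Table 19

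*SAP*

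**What the plan says.** SAP section 5.6 sets out what the pilot will supply for planning the definitive trial: the SD of weekly alcohol use, and the correlation of baseline with (i) the 180-day value and (ii) the change to 180 days, each with two-sided 80% and 90% intervals. It then describes two kinds of calculation.

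- The main one is framed as "Indicative sample sizes for a definitive trial with alcohol use at 180 days as the primary outcome" and takes the upper confidence bound for the SD. No correlation enters it.
- The additional scenarios adjust for baseline by ANCOVA and "will use the lower bound from the confidence intervals for the correlation coefficient". The singular noun does not identify which of the two correlations is meant.

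Appendix A, Table 19 has one row for each: "Correlation coefficient between baseline and 180 (± 14) days assessment of alcohol use" and "Correlation coefficient between baseline and change between baseline and 180 (± 14) days assessment of alcohol use". Both interval columns carry the asterisk, so one footnote governs both rows: "lower bound of two-sided confidence interval relevant as conservative estimate for sample size calculations".

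Table 18 lists the SD of 180-day use and the SD of change. Neither section 5.6 nor the tables say which SD goes with which correlation. Section 3.4.3 gives the proposed primary outcome of the definitive trial as "change in self-reported alcohol use (grams of pure alcohol/week) between baseline and 180" days, and protocol section 4.4 does the same, whereas section 5.6 sizes on the 180-day value.

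**The concern.** Baseline adjustment reduces the residual variance by the factor 1 − r², whatever the sign of r. A cautious planner therefore wants the smallest plausible |r|. For a positive correlation that is the lower limit. For a negative one it is the upper limit, and the lower limit is the most optimistic choice available.

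The correlation of baseline with change tends to be negative because baseline is subtracted in forming the change. The footnote therefore labels as conservative, for that row, the limit that gives the smallest sample size. Row 2 is also the row a reader would naturally use for an ANCOVA of change, the outcome named in section 3.4.3. Section 5.6 calls informing the definitive sample size a key purpose of the pilot, so the planning rule ought to do what its label says.

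**Working it through.** **Inputs from the documents.** Target 90, retention 75% (SAP section 3.5): 90 × 0.75 / 2 = 33.75, rounded down to the plan's own 33 per group, so n = 66. Interval levels are 80% and 90% (section 5.6). The documents give no correlation, SD, effect size or N for the definitive trial, so there is no plan figure to reproduce beyond this.

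**Assumed inputs.** r (baseline with 180-day use) = 0.1, 0.3, 0.5; k = SD(baseline)/SD(180) = 0.67, 1, 1.5; change = follow-up − baseline.

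**Formulas** (SD(180) = 1)
- SD(change)² = k² + 1 − 2rk
- r_bc = (r − k) / SD(change), which is negative unless r × SD(180) exceeds SD(baseline)
- ANCOVA variance = 1 − r² = SD(change)² × (1 − r_bc²)
- Limits for r_bc by Fisher's z: tanh(atanh(r_bc) ± z/√63), z = 1.282 or 1.645
- Upper SD bound, as a variance factor: 65/50.88 = 1.277 (80%); 65/47.45 = 1.370 (90%)

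**Worked case: r = 0.3, k = 1, 90% interval.** SD(change)² = 1.4 and r_bc = −0.7/1.183 = −0.592. The two rows agree at the point estimate: 1.4 × 0.650 = 0.91 = 1 − 0.3². The interval for r_bc is −0.710 to −0.441.

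| Limit used | 1 − r_bc² |
|---|---|
| Lower bound (footnote) | 0.496 |
| Point estimate | 0.650 |
| Nearest zero | 0.806 |

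The footnote's limit is 24% below the point estimate (0.496/0.650 = 0.763) and 38% below the limit nearest zero (0.496/0.806 = 0.615). At 80% the corresponding cuts are 19% and 32%. With the upper SD bound: 1.370 × 0.763 = 1.05 times the point-estimate N as written, against 1.370 × 0.806/0.650 = 1.70 intended.

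**All nine scenarios** (80% / 90%)

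| k | r | r_bc | Cut below limit nearest zero | N ÷ point-estimate N, as written with upper SD | Same, limit nearest zero |
|---|---|---|---|---|---|
| 0.67 | 0.1 | −0.50 | 27% / 33% | 1.07 / 1.08 | 1.47 / 1.63 |
| 0.67 | 0.3 | −0.36 | 21% / 26% | 1.11 / 1.14 | 1.40 / 1.53 |
| 0.67 | 0.5 | −0.19 | 12% / 15% | 1.17 / 1.22 | 1.33 / 1.42 |
| 1 | 0.1 | −0.67 | 35% / 42% | 1.01 / 1.02 | 1.56 / 1.76 |
| 1 | 0.3 | −0.59 | 32% / 38% | 1.04 / 1.05 | 1.52 / 1.70 |
| 1 | 0.5 | −0.50 | 27% / 34% | 1.07 / 1.08 | 1.47 / 1.63 |
| 1.5 | 0.1 | −0.82 | 41% / 49% | 0.97 / 0.97 | 1.65 / 1.89 |
| 1.5 | 0.3 | −0.78 | 40% / 48% | 0.98 / 0.98 | 1.63 / 1.86 |
| 1.5 | 0.5 | −0.76 | 39% / 46% | 0.99 / 0.98 | 1.61 / 1.84 |

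**In participants.** Assume a difference of 0.5 SD of 180-day use, two-sided 5%, 90% power: 2 × (1.960 + 1.282)² / 0.25 = 84.1 per arm before adjustment. With r = 0.5, k = 1 and 80% limits (r_bc −0.611 to −0.370), n per arm is 64 at the point estimate, 53 at the lower bound and 73 at the limit nearest zero. Adding the upper SD bound gives 68 against 93.

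**Row 1 for comparison.** In the same case r = 0.5 has an 80% lower limit of 0.370, which raises n per arm from 64 to 73, as intended. At r = 0.1 the 90% lower limit is −0.106, so zero should be used, but 1 − 0.106² = 0.989 against 1 is a difference of about 1%.

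**Mispairing.** If row 2's lower bound were combined with SD(180) in the worked case, the factor would be 0.496 where the correct point-estimate factor is 0.910.

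**The case against.** A reader might infer that the definitive trial's sample size is understated. The documents do not support that. No definitive N is stated. The main calculation in section 5.6 uses only the upper SD bound. The ANCOVA scenarios follow a sentence that names 180-day use as the outcome, so the natural reading is row 1, where the lower bound is right if positive. Nothing instructs the statistician to enter row 2. All of this stands, and it makes the consequence conditional.

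Three further points also carry weight. The SAP does not define the direction of subtraction: coded as a reduction (baseline minus follow-up), the correlation would usually be positive and the footnote correct. The tables' repeated label of change from baseline makes follow-up minus baseline the likelier convention, but that is an inference. Second, the upper SD bound offsets most of the error, so N would land near the point-estimate N. Third, Appendix A offers example tables, and both limits of each interval will be reported, so a later designer could choose correctly.

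None of this makes the footnote right for row 2. Section 5.6 says that it is choosing bounds conservatively, and for that row the choice removes the margin that the SD bound was meant to add.

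**Conclusion.** The rule is wrong as written for the baseline-versus-change row, under the follow-up-minus-baseline convention and unless r × SD(180) exceeds SD(baseline). It is right for the baseline/180-day row when that row's lower limit is positive, and it has no bearing on the main unadjusted calculation.

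The cost arises only if row 2 is used for an ANCOVA-of-change scenario. Over the assumed range (n = 66, r 0.1–0.5, SD ratio 0.67–1.5) the correlation term would then be about 12–41% lower than at the limit nearest zero with 80% intervals, and 15–49% lower with 90% intervals. With the upper SD bound applied as well, N would be about 0.97–1.22 times the point-estimate N, where about 1.3–1.9 times was intended. What is lost is much or all of the added caution. The sizes rest on assumed correlations and SD ratios; the direction of the error does not, once the correlation is negative. Minor to moderate: no pilot estimate, progression criterion or data collection is affected.

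**What to change.** - In section 5.6 and the Table 19 footnote, replace the lower bound with the confidence limit closest to zero, or zero if the interval spans zero. Alternatively, restrict the footnote to the baseline/180-day row.
- State that change is follow-up minus baseline.
- State that the SD of 180-day use pairs with the baseline/180-day correlation, and the SD of change with the baseline/change correlation, and name the pair that the ANCOVA scenarios will use.

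The cost is a few sentences of SAP wording and no new data. The one downside is that a quoted ANCOVA-based sample size may come out larger.
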